8.2. Investigator's Responsibilities

All reportable adverse events that occur during this follow-up phase should be fully documented in the research record by the Investigator including the onset date, complete description of the event, severity, seriousness, duration, action taken and outcome. Additional information on these events may be required. The event should be documented on the Adverse Event case report form. The investigator will be responsible for notifying the reviewing Ethics Committee (EC) / Investigational Review Board (IRB), and if applicable other authorities, of any reportable adverse events according to local regulations.

Adverse events which are possibly, probably, or definitely related to the device must be reported promptly to the sponsor. Adverse events which are unanticipated (UADE) must be reported to the sponsor by telephone or by email as soon as possible, and the completed Adverse Event CRF must be faxed to the Sponsor within 10 working days of gaining knowledge of the event together with a cover letter describing the event and detailing the medical history. The investigator shall also supply a copy of the completed Adverse Event form, together with a cover letter describing the event and detailing the medical history to the Ethics Committee. The investigator will also provide any relevant follow-up information and the outcome of the event as soon as possible.

Safety reporting: Sponsor's Responsibilities

Sponsor will provide progress reports on safety events to the Investigator to report to the EC / IRB as required. The Sponsor will also determine whether the risk analysis needs to be updated and assess whether corrective or preventive action is required.

8.3. Explantations

In the short term, explantations will usually occur due to acute/chronic infection, instability, and/or subject experiencing severe pain due to various causes. Reduced mobility alone, if it occurs, is typically not a predominant factor in prompting revision surgery. Long-term, aseptic loosening and/or severe pain may become a determining factor as to whether to proceed with device revision. Reasons for removal are not limited to these circumstances alone. The Sponsor requests Investigators to return any revised R3 Hip System components for retrieval analysis.

Explanted components are sterilized by steam autoclave or other appropriate sterilization method according to the Institution's standard sterilization procedures. Only properly packaged explants should be shipped, and the Sponsor notified before any shipment. If possible, the Sponsor will collect histological (bony ingrowth quality, bone quality, response to potential wear debris, etc.) and metallurgical (metal wear, deformation, cracking, corrosion, etc.) information from explants. For all explants, the investigator must record and forward a description of intra-operative findings including: 1) presence of

wear debris, 2) what types of hip components are being replaced, 3) and intraoperative findings relating to the device failure. Explant analysis will occur through the duration of this study.

It should be noted that the Sponsor is not always able to retrieve known explants. Some surgeons may refuse to return explants, and some institutions/hospitals will not release explanted component(s) due to their "policies."

9. Statistical Methods

Evaluations after database closure will be performed on an Intention to Treat (ITT) basis. The analysis will include the descriptive statistics of patient demographics and baseline characteristics. Accountability data will include the number of patients enrolled and the follow-up data collected. Data will be analyzed for changes from preoperative at 3 months, 1 year, 3 years, 5 years, 7 years and 10 years. Safety will be assessed by identifying and summarizing device-related adverse events throughout the study. Analysis of the success rate will be performed using Kaplan-Meier (KM) Survival Analysis. The KM estimate of the success rate along with the 95% confidence interval of the estimate will be included in the final report.

Multiple imputation techniques will be used to cope with missing data. Under the general conditions of missing at random and missing completely at random, multiple imputation result in unbiased estimates of study associations and correctly estimated standard errors and confidence intervals²⁴.

10. Monitoring Procedures

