The R3 system offers four XLPE liner options – 0 degree, 20 degree, 0 degree +4 and 20 degree +4. Conventional polyethylene will not be offered. The Smith & Nephew 10 Mrad, fully annealed XLPE is the only cross-linked polyethylene proven to produce less volume of wear debris particles in all head size ranges. Less wear debris provides a chance for reduced osteolysis.

Metal-on-metal

Early experience with metal-on-metal (MoM) bearings validated the concept of this articulation surface for THA⁹. In particular, the wear properties of MoM bearings received greater attention as the limitations of MoP bearings became known. Although the long-term success of the McKee-Farrar and Ring THA systems is attributed in part to a high carbon cobalt chrome molybdenum (CoCrMo) alloy used to produce the devices in the 'as cast' metal, reasons for failures of these devices include the limitations of manufacturing methods at the time these devices were produced¹⁰. The newer MoM prostheses utilize improved bearing geometry and new surface finishings that promote lubrication. Mid-term follow-up on these prostheses demonstrates equivalent safety and effectiveness outcome compared to MoP prostheses¹¹. They offer the potential for greatly reduced wear. Metal bearings are available in several sizes. Large femoral heads can provide increased range of motion and greater stability, which can significantly reduce the risk of hip dislocation¹².

Superior metallurgy and optimal clearances, also used in the clinically proven, highly successful, world-leading BIRMINGHAM HIP Resurfacing System (BHR), provide the R3 Metal-on-Metal system superior performance. The R3 Metal-on-Metal and the

BHR system utilize high-carbide cobalt chrome in the as-cast micro-structural condition, providing superior wear resistance. The R3 provides specific metal inserts for large femoral head sizes (Ø38mm – 54mm heads in shell sizes 50mm – 68mm) which are either combined with the modular BHR heads or the BHR resurfacing.

3. Study Objective

The objective of this study is to determine the long-term safety and effectiveness of the R3 Acetabular System

Hypothesis: implant survivorship (Kaplan-Meier) (revision for any reason) of the R3 cup is at least 97% at 3 years, 95% at 5 years, 93% at 7 years, and 90% at 10 years follow-up.

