3.2. Sample size

The target enrolment during this study is 500 patients. This number of patients leads to representative results with a greater precision of the survival rates, i.e. small confidence intervals.

The sample size is large enough to satisfy pseudo-regulatory requirements set-forth in individual European countries such as the Orthopaedic Data Evaluation Panel¹³ (ODEP) and the National Institute for Clinical Excellence (NICE) requirements¹⁴. According to the ODEP criteria for categorizing products in relation to NICE's long-term benchmarks for hip replacements, a level A study (strongest evidence) requires an initial cohort of 500 patients or more.

4. Outcome Measures

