Smith and Nephew (S&N) is performing a multicenter prospective observational post-market clinical follow-up study that will include up to 500 patients who will have total hip replacement with the R3 Acetabular System and either cemented or cementless hip stem. The objective of this study is to determine the long-term safety and effectiveness of the R3 Acetabular System. The central hypothesis is that implant survivorship of the R3 cup is at least 97% at 3 years, 95% at 5 years, 93% at 7 years, and 90% at 10 years follow-up per Kaplan Meier analysis.

Device Components

The R3 system was designed to provide the ability to tailor the implant to the individual patient requirements. The R3 system is currently available with no-hole and three-hole shells with and without HA coating and its shells have a hemispherical design. For an improved primary and secondary stability, the R3 has a porous coating called Stiktite. This coating contains sintered asymmetric titanium grains, which allows for an enhanced scratch fit and stability.

The hip system used in this study consists of R3 acetabular cups and three liner options: metal (CoCr and Oxinium), ceramic (BIOLOXforte and BIOLOXdelta) and XLPE. The modular femoral heads mate with existing, commercially-available Smith & Nephew Orthopaedics uncemented or cemented femoral stems.

Goal of Radiographic Analysis

One of the safety measures in this study is the radiographic analysis of the operated hip over time. This includes surgery- and device-related events such as device revision, component failure, malfunction, migration or loosening that can be assessed by radiograph. Some events may not be evident until after a long-term follow-up such as evidence of severe osteolysis, excessive articular surface wear, or significant debris production.

Imaging Time Points

AP and lateral radiographs will be obtained before discharge in addition to at 1 year, 3 years, 5 years, 7 years and 10 years postoperatively. Additionally, the 1-year follow-up radiograph set includes a full pelvic overview (including at least 20 cm of the proximal femur).

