3.5 Efficacy endpoints

3.5.1 Primary endpoint

The primary endpoint is implant survivorship at 10 years post study procedure.

The KM survivorship estimate for the DOD group in the PMA cohort at 3 years is 99.3% (95%CI: 97.4%-100.0%). Since this Post-Approval Study (PAS) is intended to document the long-term survivorship of the DOD treatment group only and no comparison to a control is required, no formal statistical hypothesis testing will be conducted.

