4.1 General

Categorical variables will be summarized with the number and percent of subjects in each group. Continuous variables will be summarized with the mean, standard deviation, median, minimum, and maximum values. 95% confidence intervals will be calculated for the primary and secondary endpoints.

All data collected in the CRF will be presented in the listings.

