7.1 Analysis of primary endpoint

The primary endpoint is implant survivorship at 10 years post study procedure.

Since this Post-Approval Study (PAS) is intended to document the long-term survivorship of the DOD treatment group only and no comparison to a control is required, no formal statistical hypothesis testing will be conducted.

Implant survivorship will be measured from time of surgery to time of the first instance of removal of any device component for any reason. Subjects who do not experience a removal for any reason will be censored at the date of last data collection.

Protocol Number: TBD Version 0.3

Forms					
Title Statistical Analysis Plan Template					
Code		Version	Effective Date	Page	
FRM_ST03_032		0.3	23 Apr 2015	10 of 12	

Kaplan-Meier (KM) estimates will be provided by time point (life tables) and graphically (survival curves).

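### Must the main protocol say whether the KM estimate or its lower confidence limit has to reach the 97/95/93/90% survivorship thresholds, and by which interval method?

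*Combined protocol and SAP*

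**What the plan says.** Section 3 of the main protocol (Study Objective) gives a hypothesis for Kaplan-Meier (KM) survivorship, with revision for any reason as the event: it "is at least 97% at 3 years, 95% at 5 years, 93% at 7 years, and 90% at 10 years follow-up". The Study Summary of the Image Evaluation Protocol repeats it: "The central hypothesis is that implant survivorship of the R3 cup is at least 97% at 3 years", with the same later thresholds.

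Section 3.2 justifies 500 patients by "a greater precision of the survival rates, i.e. small confidence intervals" and by a cohort-size criterion. It gives no power, significance level or target interval width. Section 9 (Statistical Methods) plans a KM analysis and says "The KM estimate of the success rate along with the 95% confidence interval of the estimate will be included in the final report".

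The SAP covers only the post-approval cohort with the delta ceramic bearing (DOD, 137 subjects). SAP 4.1 says "95% confidence intervals will be calculated for the primary and secondary endpoints", and SAP 7.1 says "Kaplan-Meier (KM) estimates will be provided by time point (life tables) and graphically (survival curves"). Neither names an interval method. SAP 3.5.1 and 7.1 and addendum 2.1 rule out formal hypothesis testing for that cohort.

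**The concern.** Four numerical thresholds labelled as a hypothesis suggest a verdict, and a verdict needs a rule. Two readings are open: the KM estimate is at or above the threshold, or the lower 95% limit is. Under the second, the answer also depends on the interval method, and common choices (linear Greenwood, log-log, exact) give different limits when survivorship is near 100%.

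The final report might then call the hypothesis met or not met on the same data, with the reading picked after the result is known. If the estimate alone counts, a cup whose true 10-year survivorship is exactly 90% is called at least 90% in about half of such studies. Under a lower-limit rule that happens in 2% to 4%.

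**Working it through.** **Inputs.** N = 500 (section 3.2); thresholds 97/95/93/90% at 3/5/7/10 years (section 3); 95% confidence level (section 9). No dropout rate is stated, so the base case assumes no censoring. KM survivorship with x revisions is then S = 1 − x/500, with Greenwood standard error SE = √(S(1−S)/500).

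**The one printed interval.** SAP 3.5.1 gives DOD survivorship "at 3 years is 99.3% (95%CI: 97.4%-100.0"%). One revision in 137 gives 1 − 1/137 = 99.27%, which matches the estimate. The lower limit from 1/137 is 97.84% (linear), 94.93% (log-log) or 96.00% (exact), none of which equals 97.4%. This does not show an error. The number at risk and the method are not stated, and a continuity-corrected limit with n = 134 gives 97.42%. A Peto standard error with about 80 at risk would also give it. No document sets this cohort against the main-protocol thresholds.

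**Lower limits at 10 years, N = 500.** Linear: S − 1.96·SE. Log-log: S^exp(1.96·v), where v = √((1−S)/(500·S)) / |ln S|. Exact: Clopper-Pearson.

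| Revisions | S | Linear | Log-log | Exact |
|---|---|---|---|---|
| 36 | 92.8% | 90.53% | 90.16% | 90.17% |
| 37 | 92.6% | 90.31% | 89.93% | 89.94% |
| 38 | 92.4% | 90.08% | 89.71% | 89.72% |
| 39 | 92.2% | 89.85% | 89.48% | 89.49% |
| 50 | 90.0% | 87.37% | 87.02% | 87.03% |

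Worked line for 38: S = 0.924, SE = √(0.924 × 0.076/500) = 0.01185, and 0.924 − 1.96 × 0.01185 = 0.9008.

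**Most revisions that still meet each threshold.**

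| Reading | 3 y | 5 y | 7 y | 10 y |
|---|---|---|---|---|
| Estimate | 15 | 25 | 35 | 50 |
| Linear lower limit | 9 | 17 | 25 | 38 |
| Log-log or exact lower limit | 7 | 15 | 23 | 36 |

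At 10 years, estimate versus limit moves the cut-off by 12 (50 − 38) or 14 (50 − 36). The interval method moves it by 2 (38 − 36). With 36 or fewer revisions every listed reading is met; above 50 none is.

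**Chance of being called met at 10 years** (exact binomial: at most 50, 38 or 36 revisions). The last column is the chance of exactly 37 or 38 revisions, where only the method decides.

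| True survivorship | Estimate | Linear | Log-log/exact | Method decides |
|---|---|---|---|---|
| 89% | 26% | 0.7% | 0.3% | 0.4% |
| 90% | 54% | 3.9% | 1.9% | 2% |
| 92% | 95% | 41% | 29% | 12% |
| 93% | 99.5% | 74% | 61% | 12% |
| 94% | 100% | 94% | 89% | 5% |
| 95% | 100% | 99.5% | 99% | 0.8% |

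Simulation with assumed dropout of 25% or 45% by 10 years gives much the same picture at a true 90%: 51% for the estimate, 3.8% to 4.2% for the linear limit and 2.0% for the log-log limit. At a true 93%, the chance of meeting a log-log lower-limit rule is 61% without dropout and 47% with 45% dropout.

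**The case for a change.** The strongest case for a change is that the sponsor chose to call this a hypothesis with four thresholds, and a final report will have to say whether they were met. Section 3.2 rests the sample size on interval width, which hints that the interval was meant to carry weight. If true 10-year survivorship is 92%, the two readings give opposite answers more often than not (95% against 41% or 29%). One sentence written before the 10-year result would remove any suspicion that the reading was picked afterwards.

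Much of this stands. The text is silent, the arithmetic is right, and the choice between estimate and limit is not trivial when survivorship lies just above 90%.

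Three things limit it. First, the plain sense of section 3 is that the KM figure itself is compared with the threshold, and section 9 plans estimation with no test, significance level or power. A success rate of about one half at exactly 90% is a property of any benchmark set on a point estimate, not a fault in the plan. Second, estimate and interval must both be reported, so the stricter reading cannot be hidden: a report with S = 91.0% shows a linear lower limit of 88.5%, below the 90% threshold. Third, a lower-limit rule would go beyond clarification. It would set a harder target than section 3.2 sized the study for. At 3 years it would also follow sight of some results, since addendum 1.1 says that 3-year DOD data were already reviewed in the premarket application.

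**Conclusion.** No change to the plan follows. This is a missing detail that the required report largely supplies: estimate and 95% interval appear together, and either standard can be read off. No stated rule gives a wrong result and no figure is shown to be miscalculated.

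At 10 years the unstated choice matters only for 37 to 50 revisions of 500 (KM 92.6% down to 90.0%), or 39 to 50 if the linear limit is used. The interval method by itself matters at two counts, 37 and 38. Outside that band all the listed readings agree. These counts assume 500 patients with no censoring. Section 9 also plans multiple imputation for missing data without saying whether it applies to survivorship, so the actual limits may differ somewhat.

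The post-approval cohort adds nothing to the case: its documents plan no test and no comparison with these thresholds. Whether to require the lower limit is a matter on which statisticians may differ in an observational follow-up study. Analysts can sensibly present the threshold comparison as descriptive, state the interval method used, and show the number at risk.

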10.1. Source Documentation

Investigators are responsible for obtaining and maintaining complete subject health information in the medical record for each subject (source documents). Examples of source documents are: hospital records, clinic and office charts, x-rays, and research subject files.

10.2. Direct Access

This study may be monitored by the Sponsor or a qualified person designated by the Sponsor. This qualified person could be an employee of the Sponsor or of a contract research organization (Sponsor's agent). The investigator will provide Sponsor, Sponsor's agents, EC / IRB and regulatory agencies with direct access to all source data/documents to permit study-related monitoring, audits, EC / IRB review, and regulatory inspections.

10.3. Interim Monitoring Visits

A clinical monitor, whether an employee of the Sponsor or its designee, has the obligation to follow this study closely. In doing so, the monitor will, in addition to maintaining necessary contact with the study site, visit the study sites at periodic intervals according to a schedule determined by the Sponsor.

10.4. Sponsor Audits and Regulatory Inspection

Quality assurance auditors, whether an employee of the Sponsor or its designee, may evaluate study conduct at the study sites. These parties must have access to any and all study reports and source documentation, regardless of location and format.

10.5. Closeout Visit

A study close out visit will be performed by the Sponsor or designee to retrieve and account for all remaining clinical data and to resolve outstanding queries, and review regulatory requirements regarding records retention and EC /IRB reporting requirements.

All activities associated with a visit (Interim Monitoring, Close out) will be documented by the monitor.

11. Data Handling and Record Keeping Requirements

Case report forms (CRFs) have been supplied by the Sponsor. Subjects will be identified by a study number and subject identification code. Only the Investigator site will have the key to identify individual subjects.

The Investigator is responsible for the timely and accurate completion of CRFs. All documents related to the study must be securely archived at the study site or in a central archive.

Data required according to this protocol are to be recorded on the case report forms(CRFs) at the time of the scheduled visits. Once a subject is enrolled, completed CRFs should be sent to the Sponsor, either by fax or by e-mail, as soon as possible.

Clinical research records shall be stored in a manner that ensures privacy, confidentiality, security and accessibility of the records both during and after the conduct of the study. The Investigator/Institution will take measures to prevent accidental or premature destruction of those documents. The investigator must retain essential study documents for at least 2 years after the latest of the following: the date the study is terminated or completed or the date the documents are no longer needed to support a premarket approval application. If the Investigator needs to dispose of the documents, the Sponsor should be contacted for approval prior to disposal or destruction. The investigator will retain these documents for a longer period if required by the applicable local laws. If the responsible investigator retires, relocates, or withdraws from responsibility of keeping the study records, custody must be transferred to a person who will accept the responsibility. The Sponsor must be notified in writing of the name and address of the new custodian. Under no circumstance shall the Investigator relocate or dispose of any study documents before having obtained written approval from the Sponsor.

12. DEVIATIONS FROM PROTOCOL

A protocol deviation is an instance of failure, intentionally or unintentionally, to follow the requirements of the protocol. Protocol deviations include, but are not limited to: study visits outside the window or missed, failure to capture patient reported outcomes using the Modified Harris Hip Score (mHHS) at defined time points, failure to conduct radiologic evaluation at defined timepoints, failure to collect adverse events at defined time points, and failure to withdraw subjects defined by protocol withdrawal measures.

12.1. Protocol Deviation Reporting Requirements

Deviations must be reported to the Sponsor as soon as reasonably possible. When protocol deviations affect the scientific soundness of the study, or the rights, safety or welfare of the study subjects, the Investigator may also need to report protocol deviations to the EC of the study site. It is the responsibility of the Principal Investigator (PI) to inform the IRB / EC of the deviation, per local requirements.

Investigators and all study staff (staff at site and at Sponsor) are responsible for ensuring adherence to study protocol. During the monitoring visits, the Sponsor representative will review all deviations with the Investigator. If a deviation is discovered outside of a monitoring visit, it should be evaluated via phone, email or letter. Appropriate measures to address the occurrence, additional monitoring visits, or audit of the study should be taken, which may include defining and implementing a Corrective and Preventive Action (CAPA).

13. Reports

Annual reports will be prepared and submitted to the EC / IRBs per the local requirements and in accordance with on-going approval requirements.

The total duration of the study is 10 years from the last subject entered. Once all of the study data is collected and the database is closed for analysis, it is anticipated that the data analysis and the preparation of a final study report will take three (3) months to complete.

14. Publication policy

